medication use (yes/no) among patients at-risk of potentially inappropriate medications, i.e., among those who may benefit from the specific EBP each month. The monthly patient-level potentially inappropriate medication use response will be summarized to clinic-level month-by-month percentage of potentially inappropriate use using administrative data from baseline to 36 months, with months 13-36 as the post-implementation follow-up period. Each trial-specific monthly data will be cross-sectional, i.e., different patients may be included in each month.

For *inappropriate polypharmacy*, the clinic-month outcome will be the proportion of patients who had medication possession (based on VA pharmacy fill data) of one or more medications from the AGS Beers criteria that are included on the VIONE PIMs dashboard [3] (numerator) among patients age 65 or older, not receiving palliative care, and followed by the clinic (denominator). For each drug included on the PIMs dashboard, there are associated business rules that define when medication use is flagged as potentially inappropriate; these same criteria will be applied in this trial. For example, use of a first or second generation anti-psychotic drug is flagged as potentially inappropriate unless there is a diagnosis of schizophrenia or bipolar disorder. These criteria had previously been determined by VIONE's Subject Matter Expert group, which provides VIONE with guidance on translating deprescribing criteria into the most practical and appropriate rules for use on the dashboard. Altogether, the following AGS Beers medications from the PIMs dashboard will be included in the analysis: anticholinergics, antipsychotics, aspirin, benzodiazepines, long-acting sulfonylureas, muscle relaxants, NSAIDs, proton pump inhibitors (PPIs), sliding scale insulin, and Z-drugs.

For *DOAC safety*, the outcome will be the proportion of patients with potentially inappropriate prescribing out of those using DOACs, as measured by "flags" (e.g., potential mis-dosing based on renal function and other indicators) on the DOAC dashboard. The DOAC flagging system is based on FDA indications and has been in clinical use since 2018. Components of the outcome include inappropriate dosing for the given indication and use of DOACs in contraindicated settings (such as valve replacements).

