For *first-line treatment for insomnia*, the outcome will be the proportion of patients with a new prescription for a sedative-hypnotic medication who have not had CBTI in the prior 12 months out of all primary care patients actively following with the clinic and are not in hospice/palliative care.

For all three trials, medication use (yes/no) and possession of active prescription for each month will be determined using exposure days based on supply days, and use will be determined by the exposure status on day 1 of each month. We will also do sensitivity analyses based on the criteria of use anytime during the month as well as PIMs defined to medications used chronically, for example, greater than 90 of the 180 prior days.

For each trial we will first compare demographic characteristics (age, sex, and race) of patients at risk of potentially inappropriate medications in the first month of implementation between the two arms. We will then obtain, for each trial by arm, crude monthly percentages (along with the corresponding 95% confidence intervals) of potentially inappropriate medications, averaged across clinics randomized to each arm and weighted by clinic-month size. For each trial, we will plot the monthly clinic level percentages over the follow-up 13-36 months to graphically assess if the difference between the two arms can be meaningfully summarized across the three trials with the unified outcome. If we find, for example, that trends between-arms over post-implementation months differ notably across the three trials, unified results comparing AD+LEAP vs. AD arm across trials may not be meaningful, and we will only conduct analyses separately by each trial.

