Secondary outcomes for VIONE will be the prevalence of potentially inappropriate use of PPIs; the prevalence of potentially inappropriate use of aspirin; and the prevalence of potentially inappropriate use of CNS active medications (muscle relaxants, anti-psychotics, Z-drugs, and

benzodiazepines) or anticholinergic drugs; number of inappropriate medications at a patient level; monthly medication costs for all drugs, without regard to appropriateness; and number of pharmacist medication reviews.

Secondary outcomes for the DOAC trial will be the sub-components of the “flags” on the dashboard. These include potential mis-dosing, potential medication interactions, or concern for nonadherence. This follows the organizational structure of both the presentation of the flags on the dashboard and the key messages provided to the academic detailing and LEAP teams. Process outcomes will be how often the provider uses the dashboard and rates of new DOAC starts compared to warfarin starts. These outcomes will be kept in alignment with our other work using the dashboard [4].

In stand-alone analyses of the CBTI trial, the primary outcome will be the prevalence of any CBTI receipt among primary care patients actively following with the clinic who are not in hospice/palliative care.

Analyses of secondary outcomes such as percent of potentially inappropriate use of PPI or mean number of CBTI sessions at each clinic month will be similar to that of the primary outcome using the GEE model accounting for correlation over time. We will also conduct separate analyses by trial with the dependent variables that are unique to each trial. For example, for the polypharmacy trial, secondary outcome of interest is count of medications flagged as inappropriate based on Beers’ criteria [3]. We will compare monthly rates of Beers’ list medication use between implementation strategies using generalized linear mixed models with log link.

Aim 3: Exploration of Potential Predictors of Clinical Outcomes

Our process evaluation will follow a multi-phase concurrent nested mixed methods design [5]. This design has three purposes: 1) help prepare all stakeholders and participants prior to the start of each trial; 2) monitor progress of implementation; and 3) explain summative findings. Overall priority is placed on quantitative methods that guide the trials, while qualitative methods are embedded or “nested” within conduct of the trials.

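### If the day-1 supply rule sets the denominator for the DOAC nonadherence flag, patients in a supply gap drop out of the outcome meant to count them

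*Combined protocol and SAP*

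**What the plan says.** Three parts of the combined protocol and SAP bear on this.

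- **Exposure rule (Aim 1: Primary Outcomes and Pooled Analysis).** One rule covers the three trials. It works from days supplied, and the main analysis takes a single reading per month: "use will be determined by the exposure status on day 1 of each month". Possession also comes from supply days, so an open order with no supply left does not count.
- **DOAC denominator (same section).** For DOAC safety, "the outcome will be the proportion of patients with potentially inappropriate prescribing out of those using DOACs". The monthly data are cross-sectional, so a patient can leave and return from month to month. The components named for this outcome concern dosing and contraindicated use; nonadherence is not named.
- **DOAC secondary outcomes (Table 1 and Aim 2: Secondary Outcomes and Analyses).** These are sub-components of the dashboard flags: "These include potential mis-dosing, potential medication interactions, or concern for nonadherence". The source is CDW administrative data. Analysis of secondary outcomes "will be similar to that of the primary outcome using the GEE model accounting for correlation over time". No flag definition, gap length, look-back period, grace period or separate denominator is given.

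Aim 1 also plans two sensitivity analyses of the exposure rule: use at any time in the month, and chronic use, for example more than 90 of the previous 180 days. Neither is tied to the nonadherence flag. The list of later changes on the cover page does not mention this outcome.

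**The concern.** In pharmacy data, nonadherence shows up as days without supply. A denominator that requires supply on day 1 therefore selects patients on the behaviour the flag is meant to detect. The mis-dosing and interaction flags do not have this difficulty, because they ask about patients who are taking the drug. One rule that suits two of the three sub-components does not suit the third.

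Two things are at stake. The level of nonadherence would be too low, or zero. The arm comparison is also exposed: refill behaviour is observed after randomisation, and if it differs by arm, so does the make-up of the denominator. Randomisation does not protect against that.

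**Working it through.** The plan gives no nonadherence rate, fill length or flag algorithm, so it has no figure to reproduce. All inputs below are assumptions, chosen to show direction and range.

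**Step 1. Flag means a current gap.** Anyone flagged has no supply on day 1 and so is outside the denominator. Measured prevalence is about 0% in both arms, whatever the truth.

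**Step 2. Flag looks back over past refills.** Let p be the true nonadherent share, q the chance that a nonadherent patient has supply on day 1, and 0.95 the same chance for other patients. Then

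measured prevalence = p·q / (p·q + (1 − p)·0.95).

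- p = 0.20, q = 0.50: 0.100 / (0.100 + 0.760) = 11.6%
- p = 0.20, q = 0.60: 0.120 / (0.120 + 0.760) = 13.6%
- p = 0.20, q = 0.70: 0.140 / (0.140 + 0.760) = 15.6%
- p = 0.20, q = 0.81: 0.162 / (0.162 + 0.760) = 17.6%
- p = 0.10, q = 0.50 to 0.70: 5.5% to 7.6%
- p = 0.30, q = 0.50 to 0.70: 18.4% to 24.0%

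The value 0.81 is a patient on 90-day fills who refills three weeks late: 90 / (90 + 21) = 0.81.

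**Step 3. A second model, with explicit refill cycles.** Nonadherent patients (20%) repeat S supplied days and g gap days at random phase; other patients are always supplied; a month is 30 days. The share of nonadherent patient-months kept by the day-1 rule is k = S / (S + g). True current-gap prevalence is 0.20·(1 − k). Measured look-back prevalence is 0.20·k / (0.80 + 0.20·k).

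| S, g (days) | Kept, day 1 | True current-gap prevalence (day-1 rule: 0%) | Look-back flag, day-1 rule (true 20%) | Kept, any time in month | Kept, >90 of 180 days |
|---|---|---|---|---|---|
| 30, 7 | 81.1% | 3.8% | 16.9% | 100% | 100% |
| 30, 15 | 66.7% | 6.7% | 14.3% | 100% | 100% |
| 30, 30 | 50.0% | 10.0% | 11.1% | 98.3% | 0% |
| 30, 60 | 33.3% | 13.3% | 7.7% | 65.6% | 0% |
| 90, 7 | 92.8% | 1.4% | 18.8% | 100% | 100% |
| 90, 15 | 85.7% | 2.9% | 17.6% | 100% | 100% |
| 90, 30 | 75.0% | 5.0% | 15.8% | 99.2% | 100% |
| 90, 60 | 60.0% | 8.0% | 13.0% | 79.3% | 79.3% |

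Both models put the bias downward.

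**Step 4. What the planned sensitivity analyses would recover, if applied here.** The any-time rule recovers gaps shorter than a month. With 60-day gaps it still loses 34% (30-day fills) or 21% (90-day fills) of nonadherent patient-months, and it loses patients who have stopped once a full month has passed without supply. The chronic-use rule, if it replaces day-1 status, drops patients with coverage of half or less but keeps many moderate cases. It also keeps a previously fully covered patient for up to 89 days after supply ends.

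**The case against.** The strongest reply is that the problem rests on two inferences. The plan does not define the flag, and it does not say that the Aim 1 exposure rule governs this Aim 2 outcome; the sentence on secondary analyses describes the model more clearly than the denominator. Aim 2 also refers to alignment with other dashboard work, and the cited source may define the flag. This stands, and the point is therefore conditional. But the exposure rule is stated for all three trials and no other denominator is offered, so carry-over is the natural reading.

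A reader might go further in four ways that the documents do not support.

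- **That the outcome misses nonadherent patients altogether.** This follows only for a current-gap flag. Under a look-back flag, patients with past gaps who are supplied on day 1 are still counted.
- **That every late refiller disappears.** Only a gap that includes a day 1 removes a patient. A 21-day gap does so about 70% of the time (21/30), and the any-time rule would keep that patient every month.
- **That the chronic-use rule selects adherent patients even more strongly.** With 90-day fills and 21-day gaps, any 180 days contain at most 42 gap days, so at least 138 covered days, and the patient is always kept. The claim is right only at coverage of half or less, or if the rule is added on top of day-1 status.
- **That the arm contrast reverses.** Raising q from 0.50 to 0.70 in one arm moves measured prevalence from 11.6% to 15.6%, but only with the true share held at 20%. If better refilling lowers that share to 15%, the result is 0.105 / (0.105 + 0.8075) = 11.5%, against 11.6%. Nor do the documents describe LEAP as refill outreach to lapsed patients.

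**Conclusion.** The point holds conditionally, for one DOAC secondary outcome. If the day-1 supply rule sets the denominator of the nonadherence flag, the outcome is about zero under a current-gap definition and understated under a look-back definition. For an assumed true 20%, the understated value is 11.6% to 15.6% at 50% to 70% day-1 coverage in nonadherent patients and 95% in others, and about 17.6% at 81% coverage. These figures are illustrative, since the plan gives no rates. Distortion of the arm comparison is possible, because inclusion depends on behaviour after randomisation, but neither its size nor a reversal is established.

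A reader might infer that the DOAC primary outcome is affected too. The plan does not show this: it measures that outcome by dashboard flags, but nonadherence is not among the components it names. This should be corrected, because a stated rule works against a named outcome and the planned sensitivity analyses neither apply to it explicitly nor recover long gaps and stops.

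**What to change.** 1. State the definition of the nonadherence flag: current gap or look-back, with the gap length or window.
2. For this flag only, use a denominator that does not require supply on day 1. One example is any DOAC fill in a fixed, prespecified look-back, no recorded discontinuation or switch to another anticoagulant, alive and followed by the clinic. Twelve months is a possible window; the documents do not favour a particular length, so use another as a sensitivity analysis.
3. Keep the day-1 rule for the mis-dosing and interaction flags.
4. Say whether the two planned sensitivity analyses apply to the nonadherence flag.
5. Say whether nonadherence flags count toward the DOAC primary outcome. If they do, add the wider denominator there as a sensitivity analysis.

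The cost is a short addition to the SAP and one changed denominator query on CDW fill data. The downside is that some patients who stopped without a recorded discontinuation will be counted, in both arms. The cover page describes analysis changes in the past tense, so results may already exist; in that case the wider denominator should be run and reported as added after the fact.

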Mixed methods analyses will be used to evaluate the following three aims:

1. *To compare the effectiveness of two implementation strategies (LEAP Quality Improvement Learning Program + Academic Detailing (AD) vs. AD alone) on potentially inappropriate medication use, using a pooled analysis of effects across three trials at 18 months, two years, and three years post-baseline at the clinic-level, based on monthly assessed data from 13-36 months;*
2. *To compare the effectiveness of the two implementation strategies on secondary outcomes specific to each trial at 18 months, two years, and three years post-baseline, based on monthly assessed data from 13 to 36 months; and*
3. *To explore the effects of implementation, provider behaviors and experiences, and context, on sustained improvements in potentially inappropriate medication use.*

Methods

Clinic Randomization

Within each trial, clinics will be randomized after assenting to participate (equivalent to enrollment). Clinics will be assigned to one of two arms by a statistician, stratified further by clinic type (medical center, community clinic, or Community Living Center) if needed to ensure partial balance between arms with respect to potential confounders associated with culture and complexities associated with clinic location [1,2].

Outcomes and Analyses

As part of a pooled analysis, we will compare the same two implementation strategies across all three EBPs and take a unified approach to implementation and evaluation across the trials. Table 1 shows MIDAS measures, data collection timeframe, and data sources. While a unified dichotomous outcome, i.e., potentially inappropriate medications, was identified for each trial to allow for the pooled analysis, each trial will also be analyzed individually (see Table 1).

Table 1: MIDAS Measures showing Data Sources and Timepoints by Aim

Aim	Type	Source
Aim 1: Primary outcome		
Service Outcomes		
Proportion of potentially inappropriate care	Quantitative	CDW administrative data
Aim 2: Secondary outcomes		
Service Outcomes		
VIONE Trial		
Potentially inappropriate use of proton pump inhibitors (PPIs), aspirin, and CNS active medications (e.g., muscle relaxants), analyzed one at a time	Quantitative	CDW administrative data
Monthly medication costs for all drugs	Quantitative	CDW administrative data
Number of pharmacist medication reviews	Quantitative	CDW administrative data

Aim	Type	Source
DOAC Trial		

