For comparison between arms, we will use generalized estimating equations (GEE) with clinic level monthly percent of potentially inappropriate medications among patients at risk during post implementation period (months 13 to 36) as the dependent variable. The model will include indicators of two trials with one trial as the referent category to account for differing underlying levels of inappropriate medication use across trials. The model will also include follow-up time in months and the LEAP+AD arm indicator with AD as the referent category and will adjust for serial correlation within clinic over time. We will also include time by arm interaction to assess if the magnitude of the difference between LEAP+AD vs. AD changes over time. If the interaction is significant, we will estimate between-arm difference at 18 months as well as at 2- and 3-years separately based on the model with the interaction term. On the other hand, if the interaction is not significant, this would indicate between-arm difference not to differ at the three follow-up times of interest (18, 24, and 36 months), and thus we will drop the interaction term and the parameter estimate of the LEAP+AD arm indicator will be used to estimate the time-averaged difference in percentage of patients with inappropriate medications during post-implementation period in clinics randomized to LEAP+AD compared to clinics randomized to AD.

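### The clinic-level GEE tests have no small-sample correction and the number of clinics is not given; with few clinics, ordinary GEE z-tests would exceed their nominal 5% error rate

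*Combined protocol and SAP*

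**What the plan says.** The Clinic Randomization section makes the clinic the unit of allocation, separately in each trial: "Within each trial, clinics will be randomized after assenting to participate (equivalent to enrollment". In the Aim 1 section the arm comparison is a GEE on clinic-month percentages: "we will use generalized estimating equations (GEE) with clinic level monthly percent of potentially inappropriate medications". On the mean structure, "The model will include indicators of two trials with one trial as the referent category"; time, arm and time-by-arm are added. On variance, the text says only that the model "will adjust for serial correlation within clinic over time". The significance of the time-by-arm term decides whether effects at separate time points or one time-averaged effect is reported.

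Single-trial analyses are also planned. Under Outcomes and Analyses, "each trial will also be analyzed individually". If between-arm trends differ notably across trials, the Aim 1 section says "we will only conduct analyses separately by each trial". Under Aim 2, analyses of secondary outcomes such as the percentage with inappropriate PPI use "will be similar to that of the primary outcome using the GEE model accounting for correlation over time".

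The documents do not give the number of clinics, the allocation ratio, the significance level of the tests, the working correlation, the type of standard error or the reference distribution. The cover note reports that follow-up ended at 18 months. It also says the arm difference was modelled as a single outcome, adjusted for EBP and pre-period level, and names no estimator.

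**The concern.** The independent unit is the clinic, so the information about arm comes from the number of clinics and not from the number of patients or months. The usual GEE sandwich variance is built from squared residuals without allowance for the fitted parameters, so it is biased downward when clusters are few. Referring the result to a normal distribution then ignores the uncertainty in that variance. Both faults make intervals too narrow and p-values too small.

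The effect is largest where clinics are fewest, which is in the single-trial analyses. These matter most if pooling is abandoned, because they are then the only analyses of the primary outcome. An anti-conservative time-by-arm test would also affect which estimate is reported.

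**Working it through.** The plan states no power, sample size or error rate, so there is no figure of its own to reproduce. The check runs over a range of clinic counts.

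**Inputs from the document:** randomization by clinic within trial; GEE on clinic-month percentages; in the pooled model, four clinic-level parameters (intercept, arm and two trial indicators).

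**Assumed, because not stated:** two-sided 5%; 1:1 allocation; balanced clinics; identity link; approximately normal clinic means; sandwich variance with a z reference; 6 to 100 clinics per trial (18 to 300 pooled).

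**One trial.** Let *m* be clinics per arm. With balanced data the arm coefficient is a difference of clinic means, and the uncorrected sandwich variance is (m−1)/m of the unbiased one. The true size of the nominal 5% test is

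P(|t with 2m−2 df| > 1.96 × √((m−1)/m)).

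For 6 clinics, m = 3: 1.96 × √(2/3) = 1.60, and P(|t₄| > 1.60) = 18.5%. The standard error is √(2/3) = 0.816 of its proper value.

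For 20 clinics, m = 10: 1.96 × √0.9 = 1.86, and P(|t₁₈| > 1.86) = 7.9%.

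**Pooled.** With N clinics and four clinic-level parameters, a close approximation is

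P(|t with N−4 df| > 1.96 × √((N−4)/N)).

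For N = 18: 1.96 × √(14/18) = 1.73, and P(|t₁₄| > 1.73) = 10.6%.

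| Clinics in one trial | Size | Clinics pooled | Size |
|---|---|---|---|
| 6 | 18.5% | 18 | 10.6% |
| 10 | 11.8% | 30 | 8.0% |
| 20 | 7.9% | 60 | 6.4% |
| 30 | 6.9% | 120 | 5.6% |
| 60 | 5.9% | 300 | 5.3% |
| 100 | 5.5% | | |

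**Check with fitted GEEs.** These were null simulations with 1,500 replicates, six months of data, exchangeable working correlation and the arm main effect only. Robust z-tests rejected in 15.5%, 12.1% and 8.3% at 8, 12 and 20 clinics in one trial, and in 9.3% and 5.7% at 24 and 48 clinics pooled. The closed form gives 14.0%, 10.4%, 7.9%, 8.9% and 6.7%, which agrees within simulation error of one to two points. Model-based standard errors with z gave 14.9%, 11.6% and 8.1% in the single-trial cases, so switching to them does not solve the problem. The time-by-arm test was not simulated; the same mechanism applies, since it compares clinic slopes between arms.

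**After correction.** In 40,000-replicate simulations of clinic means, Kauermann-Carroll variance with t on clinics minus clinic-level parameters gave 4.5% to 5.2% across 6 to 60 clinics per trial and 18 to 180 pooled. Mancl-DeRouen with t gave 2.6% to 4.6% for one trial and 2.9% to 4.8% pooled, which is conservative.

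**Cost in interval width.** The corrected interval is wider by √(m/(m−1)) × t/1.96:

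- 6 clinics: 1.225 × 2.776/1.96 = 1.73, or 73% wider.
- 20 clinics: 1.054 × 2.101/1.96 = 1.13, or 13% wider.
- 100 clinics: 1.010 × 1.984/1.96 = 1.02, or about 2% wider.

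**The case against.** The strongest objection is that the plan does not say its tests are uncorrected. It is silent on the type of standard error, the reference distribution and the significance level, and the clinic count behind every figure above is assumed. A reader might infer that the trial's standard errors are too small and its false-positive rate is above 5%. The documents do not support that: a correction may have been used, and with about 100 clinics per trial, or several hundred pooled, the inflation nearly disappears. If randomization was stratified by clinic type and the strata are left out of the model, standard errors could also be pushed upward. All of this stands, and it makes the point conditional. It does not remove it, because a prespecified analysis should fix the inference method, and ordinary GEE output run as written is anti-conservative when clinics are few.

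A second objection is that the cover note replaced the primary model. This also stands. If the single-outcome model was linear with a t reference, the primary result is unaffected; if it used robust or z-based inference, the problem carries over. The cover note does not say which, and it does not alter the GEE method for the remaining secondary outcomes.

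A third concerns scope. A reader might infer that every single-trial and secondary analysis is affected. The Beers medication count uses a GLMM with log link, and the two CBTI outcomes dropped in the cover note are not analyzed; none of these is covered. The sentences providing for single-trial analyses do not name GEE, so its use there is a presumption, though a natural one. The patient-level GLMM planned in case of demographic imbalance is a different analysis and supplies no correction for the GEE.

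**Conclusion.** The point holds in conditional form. The plan rests its arm and time-by-arm tests on clinic-level GEE and specifies neither the clinic count nor any small-sample method. If default z-tests are used, the inflation is serious at roughly 6 to 20 clinics per trial (about 18% falling to 8%), modest at 30 to 60 (about 7% falling to 6%), and close to nil at 100. Pooling lessens it but does not remove it at small totals.

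These sizes rest on the assumed 5% level, 1:1 allocation, balanced clinics and no omitted strata. The documents do not show where in this range the trial lies, or that any reported result is wrong. It is a change that should be made, because it costs little and protects the single-trial analyses in particular.

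**What to change.** State that every GEE test of arm and of time-by-arm uses a Kauermann-Carroll bias-corrected sandwich variance, with a t reference on clinics minus clinic-level parameters. Report the number of clinics per trial and arm. Kauermann-Carroll is preferable to Mancl-DeRouen here because the latter, combined with t, is conservative.

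For the cover note's single-outcome model, state the estimator and how the standard error was computed. Apply the same correction only if inference was robust or z-based; a linear model with a t reference needs no change.

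A permutation test of arm within randomization strata is an optional check for single-trial analyses. It is useful only where enough allocations exist to reach p < 0.05: three clinics against three gives 20 allocations and a smallest two-sided p of 2/20 = 0.10.

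The cost is a sentence in the plan, a software option and a rerun on the existing data. Intervals widen negligibly with many clinics and substantially with very few. In the latter case the added width reflects the real uncertainty.
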